### **8.1.2.3 Sensitivity Analysis**

As sensitivity analyses, the difference in the percentage of subjects in the mITT-GT and mITT-GT-VF populations achieving SVR12 between Arm A and Arm B in non-cirrhotic subjects, and between Arm C and Arm D in cirrhotic subjects, as applicable, will be summarized. The SVR12 rates in the EP-RS-GT and EP-RS-GT-VF populations overall will be calculated.

### **8.1.2.4 Subgroup Analysis**

In the mITT population for the Main study, association of the proportions of subjects with SVR12 with each of the following subgroups will be compared across treatment arms (Arms A and B, and Arm C and D separately) using Zelen's exact tests. In addition, two-sided 95% Wilson score intervals will be calculated for the difference between Arms A and B and Arms C and D, for the following subgroups:

- HCV GT1 subtype;
- Most recent HCV treatment history;
- All prior HCV treatment history;
- Type of non-response to NS5A-inhibitor+SOF± RBV treatment;
- Sex;
- Age;
- Race;
- Ethnicity;
- BMI;
- Baseline HCV RNA level;

- Baseline platelet count;
- Baseline albumin;
- Baseline APRI;
- Baseline FIB-4;
- Baseline AST/ALT ratio;
- Baseline Child-Pugh Score (for cirrhotic subjects only);
- History of concomitant diseases: (a) diabetes, (b) HIV coinfection (c) post-organ transplant;
- Concomitant use of Proton Pump inhibitors
- DAA compliance.
- Baseline resistance polymorphisms (any NS3/4A variant [yes/no]; any NS5A variant [yes/no]; any NS3/4A and any NS5A [yes/no], any NS3/4A or any NS5A [yes/no]) and [NS3/4A only, NS5A only, both NS3/4A and NS5A, or none]).

The difference in SVR12 rates between G/P given for 12 weeks (Arm A and C combined) and G/P given for 16 weeks (Arm B and D combined) will also be examined within the combined arms by HCV sub-genotype (1b vs. non-1b).

Further details about subgroup analyses will be described in the Statistical Analysis Plan.

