**Main Exclusion:**

1. History of severe, life-threatening or other significant sensitivity to any drug.
2. Female who is pregnant, planning to become pregnant during the study or breastfeeding; or male whose partner is pregnant or planning to become pregnant during the study.
3. Clinically significant abnormalities or comorbidities or recent (within 6 months prior to study drug administration) history of drug or alcohol abuse that make the subjects an unsuitable candidate for this study in the opinion of the investigator.
4. Positive test result at Screening for hepatitis B co-infection (HBsAg positive or Hep B Core Ab -Total positive with detectable HBV DNA) or anti-human immunodeficiency virus antibody (HIV Ab) in patient without known history of HIV+ and stable HART therapy\*.
5. Prior therapy with HCV PI at any time\*.
6. History or presence of liver decompensation.

\*Applicable during Screening for the Main study only.

Study Drug(s)	Glecaprevir/pibrentasvir 100 mg/40 mg Tablet Ribavirin 200 mg Tablet*** *Sofosbuvir 400 mg Tablet ***Ribavirin Dosage Form to be determined by dispensing pharmacy during Retreatment sub-study
Doses:	Glecaprevir Dose: 300 mg QD Pibrentasvir Dose: 120 mg QD Glecaprevir/pibrentasvir tablets: 300 mg/120 mg QD (3 tablets) Ribavirin tablets***: 1000 to 1200 mg total daily dose divided into two doses BID (5 or 6 tablets total daily dose) at the discretion of the PI * Sofosbuvir 400 mg QD
Mode of Administration:	Oral with food for glecaprevir/pibrentasvir, ribavirin, and *Sofosbuvir
Reference Therapy:	N/A
Duration of Treatment:	Main Study treatment duration is 12 weeks in Arms A and C, and 16 weeks in Arms B and D. Retreatment sub-study treatment duration is 16 weeks. * For Retreatment sub-study only
Criteria for Evaluation:	
Efficacy:	Efficacy will be assessed by plasma HCV RNA levels throughout the study.

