#### **5.4.1.1 Virologic Stopping Criteria**

##### **Individual Patient**

Virologic stopping criteria are defined as one of the following:

1. Confirmed HCV RNA  $\geq 100$  IU/mL (defined as 2 consecutive HCV RNA measurements  $\geq 100$  IU/mL) after HCV RNA  $<$  LLOQ during treatment.
2. Confirmed increase from nadir in HCV RNA (defined as 2 consecutive HCV RNA measurements of  $> 1 \log_{10}$  IU/mL above nadir) at any time point during treatment,

When confirmatory testing is required it should be completed as soon as possible and the subject should remain on study treatment until the virologic stopping criteria has been confirmed. Subjects meeting virologic stopping criteria will be discontinued from study drug and will continue to be followed in the Post-Treatment Period for the emergence and persistence of resistant viral variants until 12 weeks post-treatment.

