### **5.5.7                   Treatment Compliance**

The investigator or his/her designated and qualified representatives will administer/ dispense study drug only to subjects enrolled in the study in accordance with the protocol. The study drug must not be used for reasons other than that described in the protocol.

At the start of the study, each subject should receive counselling regarding the importance of dosing compliance with the treatment regimen with regard to virologic response and potential development of resistance due to poor compliance.

At each study drug dispensing visit during the Treatment Period denoted in **Table 5**, subjects will be instructed to bring all study drug (full, partial or empty) for assessment of treatment compliance. Subjects will be instructed to dose from each bottle of study medication until the bottle is empty. At post-baseline dispensing visits denoted in **Table**

6, study site personnel will assess subject compliance by inspecting the contents of the bottles and record the status of each one, as well as the exact number of remaining tablets\*\*\* of G/P and/or RBV in the source. Treatment compliance will be based on the number of tablets\*\*\* dispensed, as recorded in source and the number of remaining tablets\*\*\*.

\*\*\*RBV Dosage form to be determined by dispensing pharmacy.

Dosing compliance will also be assessed for patients receiving treatment in the Retreatment sub-study. In addition to G/P and RBV, accounting of SOF dosing will be completed and recorded in the study source.

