### **8.1.1 Demographics**

Demographics and baseline characteristics will be summarized for all treated subjects by treatment arm for the Main Study and separately on the overall EP-RS population.

Demographics include age, weight, height, BMI, gender, race, and ethnicity. Baseline characteristics will be summarized as continuous variables (where appropriate) and as categorical variables, including HCV genotype subtype, most recent HCV treatment history, baseline HCV RNA level, and fibrosis stage.

Summary statistics (N, mean, median, SD, and range) will be generated by treatment arm for continuous variables (e.g., age and BMI), and the number and percentage of subjects will be presented for categorical variables (e.g., sex and race).

Study drug exposure and compliance will be summarized by treatment arm and separately on the overall EP-RS population. Treatment compliance to study drug will be calculated based on the percentage of tablets\*\*\* taken relative to the total tablets\*\*\* expected to be taken for each tablet\*\*\* type G/P, RBV, SOF tablets as applicable. A subject is considered to be compliant if the percentage is between 80% and 120% for each tablet type. Compliance will be calculated for each subject and summarized with the mean, median, standard deviation, minimum, and maximum. The percentage of compliant subjects will be summarized.

\*\*\*RBV Dosage Form to be determined by dispensing pharmacy.

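### DAA compliance, a post-randomisation variable, is listed as a subgroup factor for between-arm SVR12 contrasts

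*Protocol*

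**What the plan says.** Section 8.1.2.4 lists 20 factors for SVR12 in the mITT population, one of which is "DAA compliance". For every factor, Zelen's exact test is to be used for A with B and for C with D separately. In addition, "two-sided 95% Wilson score intervals will be calculated for the difference between Arms A and B and Arms C and D". The choice of factor and its use for arm contrasts are therefore fixed in the protocol; only further detail is left to the SAP.

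Section 8.1.1 defines compliance as tablets taken relative to those "expected to be taken for each tablet" type, and adds: "A subject is considered to be compliant if the percentage is between 80% and 120% for each tablet type". Section 5.5.7 gives the source of the data: "Treatment compliance will be based on the number of tablets" dispensed and the number remaining. These are counts made at visits during treatment.

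Two further provisions matter. The synopsis states: "Main Study treatment duration is 12 weeks in Arms A and C, and 16 weeks in Arms B and D". Section 5.4.1.1 states: "Subjects meeting virologic stopping criteria will be discontinued from study drug".

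**The concern.** A subgroup contrast between randomised arms keeps the benefit of randomisation when the subgroup is fixed before treatment. Nearly all the other entries in Section 8.1.2.4 are demographic, historical or pre-treatment, and eight are expressly labelled as baseline. Compliance is different. It is behaviour under the assigned regimen, and the regimens compared have different planned lengths. Subjects who stay compliant over 12 weeks are not necessarily the same kind of subject as those who stay compliant over 16.

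Depending on how expected tablets are counted, the outcome may also help to decide the subgroup, because virologic failure on treatment leads to stopping the drug.

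The study asks whether treatment can be shortened. An arm difference among compliant subjects is easily read as the effect in patients who took the drug properly, and the planned contrast cannot support that reading.

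**Working it through.** The plan gives no figure for this point, so there is none to reproduce. The check has four steps.

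**1. When the factor is measured.** Sections 5.5.7 and 8.1.1 build it from tablet counts during treatment, after randomisation. This holds whatever denominator is used.

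**2. Denominator = planned course (an assumption; Section 8.1.1 does not say).** G/P is three tablets once daily with no dose adjustment (Section 5.5.1). A fully adherent subject stopped after d days therefore has compliance d / planned days.

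- Arms A and C: 12 × 7 = 84 days; 0.80 × 84 = 67.2 days (week 9.6). 67/84 = 79.8%; 68/84 = 81.0%.
- Arms B and D: 16 × 7 = 112 days; 0.80 × 112 = 89.6 days (week 12.8). 89/112 = 79.5%; 90/112 = 80.4%.

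| Stop for virologic failure | 12-week arm | 16-week arm |
|---|---|---|
| Week 8 | 8/12 = 66.7%, non-compliant | 8/16 = 50.0%, non-compliant |
| Week 10 | 10/12 = 83.3%, compliant | 10/16 = 62.5%, non-compliant |
| Week 12 | 12/12 = 100%, compliant | 12/16 = 75.0%, non-compliant |

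The same adherence and the same failure time can thus give a different label in the two arms. The visit schedule makes such stops possible: HCV RNA is drawn at Weeks 4, 8 and 12 (and 16 in Arms B and D), and a stop follows confirmation.

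**3. Denominator = days up to the stop.** Compliance of the same subject is d / d = 100% for any d. The mechanical link with failure is gone. Step 1 is unchanged.

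**4. Possible size under step 2, illustration only.** Assume true SVR12 of 94% in both arms (Section 8.2 cites 94.4% for 16 weeks), 6% failures, of which f points are on-treatment failures stopped equally at Weeks 8, 10 and 12, and full adherence otherwise. SVR12 among compliant subjects is 94/(100 − f/3) in the 12-week arm and 94/(100 − f) in the 16-week arm.

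- f = 0: 94.0% and 94.0%; difference 0.
- f = 3: 94/99 = 94.9% and 94/97 = 96.9%; difference 2.0 points.
- f = 6: 94/98 = 95.9% and 94/94 = 100%; difference 4.1 points.

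Timing matters as much as frequency. With f = 3 and all stops at Week 8, both arms give 94/97 = 96.9% and the difference is 0. With all stops at Week 10 or 12, the figures are 94.0% and 96.9%, 2.9 points against the shorter course. If stops came at Week 8 in the 12-week arm but after day 90 in the 16-week arm, the 2.9 points would favour the shorter course. The documents fix neither the size nor the direction.

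**The case against.** The strongest reply is that the link between failure and compliance status depends on a denominator the protocol does not give. A subject taken off drug can fairly be said to be expected to take tablets only until then, and a compliance denominator is a normal SAP item. This stands: the missing definition is not itself a fault, and the day-67 and day-90 cuts are conditional on one reading. It does not answer the first step, because the protocol itself chose an on-treatment variable for between-arm contrasts.

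A second reply is that the matter is small, and this also stands. The primary analysis uses all treated subjects, and no success criterion rests on a subgroup. An illustrative 2 points is well inside the half-widths planned in Section 8.2 for the full comparisons (0.067 to 0.095 for A and B, 0.061 to 0.112 for C and D). In the earlier study summarised in Section 3.4, 30/31 non-cirrhotic subjects reached SVR12, so few early stops might be expected in Arms A and B. Both failures among the 11 cirrhotic subjects were on-treatment, but 11 is too few to project from.

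A third reply is that defining the denominator and labelling the analysis exploratory would be enough. That would remove the mechanical link but leave arm contrasts that randomisation does not protect.

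Some stronger readings are tempting but not supported:

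- A reader might infer that the compliant subgroup is emptied of virologic failures. It is not. Relapses remain in it, and so do subjects with quantifiable HCV RNA at the end of a completed course, whom Section 8.1.2.2 counts as on-treatment failures.
- A reader might infer that Zelen's test compares arms within a compliance level. It tests homogeneity across strata; only the Wilson intervals are within-level contrasts. Both condition on the post-randomisation variable.
- A reader might infer that ribavirin in Arm C distorts compliance there. The listed factor concerns DAAs, ribavirin is not one, and nothing in the protocol shows an effect on G/P tablet-taking.
- A reader might extend the point to proton pump inhibitor use in the same list. The protocol does not say when that use is taken, so no problem is shown.

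**Conclusion.** The point holds in a limited form. Section 8.1.2.4 fixes a post-randomisation variable as a factor for contrasting SVR12 between randomised arms of different planned length, so those contrasts lack the protection of randomisation under either denominator. That part needs no assumption.

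The further claim, that failure itself sets compliance status and does so differently by arm, holds only if expected tablets mean the planned course. The two cuts then lie 89.6 − 67.2 = 22.4 days apart. That gap measures differential labelling; it is not an estimate of bias in SVR12. The differences of 0 to about 4 points shown above rest on assumed failure rates and stop times.

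The consequence is confined to one of 20 supportive factors. It is a minor improvement and gives no reason to doubt the primary or secondary analyses.

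**What to change.** Delete the DAA compliance entry from the between-arm subgroup list in Section 8.1.2.4. In its place, report SVR12 by compliance category descriptively within each arm, without a test or interval for the arm difference. Count expected tablets from Day 1 to the actual day treatment stopped, and state this beside the definition in Section 8.1.1.

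The cost is one deleted line, one sentence of definition and one descriptive table. No new data are needed: tablet counts are already collected, and Section 5.4.1 already has the last dose and the reason for discontinuation recorded.

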#### **8.1.2.5 Additional Efficacy Endpoints**

The following additional efficacy endpoints will be summarized for each treatment arm in the mITT population and overall in the EP-RS population, as specified below:

- The percentage of mITT subjects with HCV RNA < LLOQ at each post-baseline visit in the Treatment Period (using data as observed);
- The percentage of mITT subjects with SVR4;
- The percentage of EP-RS subjects achieving SVR12.
- The percentage of EP-RS subjects with on-treatment virologic failure and with post-treatment relapse.

In the above analyses for SVR, the percentage of subjects and a two-sided 95% Wilson score interval will be summarized. A summary of reasons for SVR non-response will also be provided for subjects in the EP-RS populations who do not achieve SVR12.

### **8.1.3 Resistance Analyses**

The following analyses will be performed for all subjects in the mITT population and the EP-RS populations separately. In the EP-RS population, baseline polymorphisms in NS3 and NS5A will be reassessed prior to treatment with G/P + SOF  $\pm$  RBV.

The HCV NS3 and NS5A amino acid sequences from baseline samples as determined by population sequencing or NGS will be compared to the appropriate prototypic reference sequence. A listing by subject of all baseline polymorphisms relative to prototypic reference sequence at signature amino acid positions will be provided for each DAA target (NS3 and NS5A).

The following analyses will be performed for subjects who do not achieve SVR12 and who have post-baseline resistance data available:

(1) The HCV NS3 and NS5A amino acid sequences from the sample closest in time after virologic failure or treatment discontinuation with an HCV RNA level of  $\geq 1000$  IU/mL as determined by population sequencing or NGS will be compared to the baseline sequence. A listing by subject of all post-baseline substitutions at signature amino acid positions relative to the baseline amino acid sequence will be provided for each DAA target (NS3 and NS5A).

(2) The HCV NS3 and NS5A amino acid sequences from the sample closest in time after virologic failure or treatment discontinuation with an HCV RNA level of  $\geq 1000$  IU/mL will be compared to the appropriate prototypic reference sequence. A listing by subject of

all post-baseline substitutions at signature amino acid positions relative to the appropriate prototypic reference amino acid sequence will be provided for each DAA target (NS3 and NS5A).

(3) The persistence of post-baseline substitutions at signature amino acid positions for each target (NS3 and NS5A) will be assessed by population sequencing or NGS at Post-Treatment Week 12. A listing by subject and time point of all substitutions relative to the baseline amino acid sequence will be provided for each DAA target (NS3 and NS5A).

For subjects who experience virologic failure in the Retreatment sub-study, the NS3, NS5A, and NS5B sequences from the baseline sample and from the sample closest in time after virologic failure with an HCV RNA level of  $\geq 1000$  IU/mL will be evaluated as described in analyses (1) and (2) above.

#### **8.1.4 Adverse Events**

All subjects who receive at least one dose of study drug will be included in the safety analyses. Safety analyses will be conducted separately for the Main study and the Retreatment sub-study.

Adverse events will be coded using the Medical Dictionary for Regulatory Activities (MedDRA). The number and percentage of subjects with treatment-emergent adverse events (i.e., any event that begins or worsens in severity after initiation of study drug through 30 days post-study drug dosing) will be tabulated by primary MedDRA System Organ Class (SOC) and preferred term (PT) for each treatment arm. The tabulation of the number of subjects with treatment-emergent adverse events by severity grade and relationship to study drug also will be provided. Subjects reporting more than one adverse event for a given MedDRA preferred term will be counted only once for that term using the most severe grade for the severity grade table and the most related for the relationship to study drug table. Subjects reporting more than one type of event within a SOC will be

counted only once for that SOC. Selected adverse events will be summarized separately for the Re-treatment Substudy.

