**Number of Subjects to be Enrolled:** up to 225 subjects**\*Applicable to Retreatment sub-study only**

**Methodology:**

**Main Study:**

This is a Phase 3b, randomized, open-label, pragmatic, multicenter study to evaluate efficacy and safety of the fixed-dose combination tablets of glecaprevir/pibrentasvir with or without RBV in NS5A-inhibitor plus sofosbuvir ± RBV-experienced, chronic HCV GT1-infected subjects. Up to 225 subjects at approximately 35 sites will be enrolled into four study arms A, B, C and D. Up to 150 non-cirrhotic subjects will be randomized in a 2:1 ratio to Arms A and B, and up to 75 subjects with compensated cirrhosis will be randomized in a 1:1 ratio to Arms C and D. Randomization will be stratified by HCV genotype 1 subtype (1b or non-1b).

Subjects without cirrhosis will be randomized 2:1 to:

Arm A: G/P 300 mg/120 mg QD for 12 weeks

Arm B: G/P 300 mg/120 mg QD for 16 weeks

Subjects with compensated cirrhosis will be randomized 1:1 to:

Arm C: G/P 300 mg/120 mg QD + weight-based RBV BID (1000 mg or 1200 mg total daily dose) for 12 weeks

Arm D: G/P 300 mg/120 mg QD for 16 weeks

Subjects who complete or prematurely discontinue the treatment will be followed for 12 weeks to monitor HCV RNA and to evaluate efficacy and the emergence and persistence of viral variants.

Scheduled visits for subjects in the planned Treatment Period consist of Day 1, Weeks 4, 8, 12 for all subjects and Week 16 for subjects in Arms B and D. During the Post-Treatment Period, subjects will have visits at Weeks 4 and 12 following completion of the Treatment Period. Efficacy and safety data will be monitored throughout the study. These data will enable assessment of virologic stopping, futility, and treatment extension criteria as described in the protocol.

---

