### **8.1.5 Clinical Laboratory Data**

Clinical laboratory tests will be summarized at each visit by treatment arm. The baseline value will be the last non-missing measurement prior to the initial dose of study drug. Mean changes from baseline to each post-baseline visit, including the Final Treatment Visit, will be summarized descriptively for each treatment arm.

In addition, the number and percentage of subjects with post-baseline laboratory values showing increase in CTCAE toxicity grade during treatment will be summarized by treatment arm for the Main study and overall for the Retreatment sub-study.

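### Minor: crude per-arm percentages for AEs and CTCAE grade increases cover longer windows in the 16-week arms, so the Arm C vs Arm D contrast for ribavirin leans toward no difference; a common-window table would fix this cheaply

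*Protocol*

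**What the plan says.** The Synopsis sets the durations: "Main Study treatment duration is 12 weeks in Arms A and C, and 16 weeks in Arms B and D". The two cirrhotic arms are "Arm C: G/P 300 mg/120 mg QD + weight-based RBV BID (1000 mg or 1200 mg total daily dose) for 12 weeks" and "Arm D: G/P 300 mg/120 mg QD for 16 weeks".

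Section 8.1.4 defines a treatment-emergent event as "any event that begins or worsens in severity after initiation of study drug through 30 days post-study drug dosing". The number and percentage of subjects with such events "will be tabulated by primary MedDRA System Organ Class (SOC) and preferred term (PT) for each treatment arm". The window and the tabulation stand in one sentence of that section: "after initiation of study drug through 30 days post-study drug dosing) will be tabulated by primary MedDRA System Organ Class". A subject counts once per preferred term and once per organ class. There are further tables by severity and by relationship to study drug.

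Section 8.1.5 does two things. It summarizes laboratory tests at each visit by arm, with mean change from baseline. It also reports "the number and percentage of subjects with post-baseline laboratory values showing increase in CTCAE toxicity grade during treatment", by arm.

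Section 8.1.1 summarizes exposure per arm but does not link it to the AE tables. Section 4.1 lists safety and tolerability with or without ribavirin among the primary objectives. No between-arm safety test is specified; the summaries are descriptive.

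**The concern.** A once-per-subject percentage depends on the event rate and on how long the subject is watched. Here the length of observation is part of the arm, so a difference between two arms mixes the two.

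This matters most for Arm C vs Arm D, the only randomized contrast in which ribavirin is planned in one arm and not the other. The ribavirin arm has the shorter window, so the crude difference understates a ribavirin excess in the event rate. In Arm A vs Arm B, a lower percentage after 12 weeks could be read as a lower rate per unit of treatment when it reflects only less time to record events.

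At stake is how the C vs D and A vs B safety tables are interpreted, not the validity of any planned test.

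**Working it through.** **Windows (Synopsis durations; Sections 8.1.4 and 8.1.5)**

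- AEs: 12 × 7 + 30 = 114 days in Arms A and C; 16 × 7 + 30 = 142 days in Arms B and D. Ratio 142/114 = 1.246.
- Laboratory shifts, treatment only: 84 and 112 days. Ratio 112/84 = 1.333. Table 5 schedules three post-baseline on-treatment draws (Weeks 4, 8, 12) against four (plus Week 16).

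**The plan's own precision figure**

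The protocol gives no figure for observation time or safety precision. The nearest is the Section 8.2 half-width for C vs D SVR12 with 40 per arm and both rates 94%: 1.96 × √(2 × 0.94 × 0.06/40) = 0.104, as printed. The same formula is used below to judge scale.

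**Model (assumption)**

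Constant hazard: p = 1 − exp(−rate × window). The protocol gives neither a hazard shape nor event rates for these arms, so a range is shown.

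**Equal true rates in C and D**

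| Arm C crude | Arm D crude, AEs | Arm D crude, laboratory shifts |
|---|---|---|
| 10% | 12.3% | 13.1% |
| 20% | 24.3% | 25.7% |
| 30% | 35.9% | 37.8% |
| 50% | 57.8% | 60.3% |

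The gap produced by time alone is about 2 to 8 points for AEs and 3 to 10 points for laboratory shifts. The crude difference is zero when the C/D rate ratio equals the window ratio, 1.25 or 1.33.

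**True excess in Arm C, AEs, Arm D crude at 20%**

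Daily rate in D = −ln(0.80)/142 = 0.001571. Over 84 days D shows 1 − exp(−84 × 0.001571) = 12.4%. Arm C uses the same formula with the rate multiplied by the ratio.

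| Rate ratio C/D | Crude C vs D | Difference (ratio of percentages) | Both over 84 days | Difference (ratio of percentages) |
|---|---|---|---|---|
| 1.25 | 20.1% vs 20.0% | +0.1 (1.00) | 15.2% vs 12.4% | +2.8 (1.23) |
| 2 | 30.1% vs 20.0% | +10.1 (1.51) | 23.2% vs 12.4% | +10.8 (1.88) |
| 3 | 41.6% vs 20.0% | +21.6 (2.08) | 32.7% vs 12.4% | +20.3 (2.64) |

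Over a common 114 days the differences at ratios 2 and 3 would be +13.7 and +25.2 points. The 84-day table discards events after Week 12, so its gain shows in the ratio more than in the absolute difference.

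**A high-frequency example**

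Table 3 gives 67.5% with any AE for pooled G/P regimens. Taking that as Arm D's 142-day figure (an assumption) with a rate ratio of 1.25, the crude table shows 67.6% vs 67.5%, a common 114-day window 67.6% vs 59.4%, and the 84-day table about 56% vs 49%.

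**Precision**

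With 40 per arm and crude AE percentages of 10% to 50%, the half-width of a 95% interval for the difference is about 13 to 22 points.

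**The case against.** The strongest reply has four parts.

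*The whole-regimen percentage is a proper quantity.* Duration is part of what is randomized. If 16 weeks leaves more subjects with an event, that is a real cost of the regimen. This stands, and it is why the existing tables should remain. A reader might infer that Section 8.1.4 is wrong or that it invents an advantage for 12 weeks; the text does not support that. The limitation appears only when a difference is attributed to ribavirin or to the rate per unit of treatment.

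*The main ribavirin toxicity is already covered at matched times.* Section 3.6 names hemolytic anemia, and Section 8.1.5 summarizes laboratory tests, including hemoglobin, at each visit by arm, hence at Weeks 4, 8 and 12 in both C and D. AEs are also split by severity and relationship. This stands as well and confines the point to the AE tables and the CTCAE-shift percentages. Visit means do not replace counts of subjects with a grade increase.

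*The size depends on assumptions.* Exact cancellation needs a rate ratio equal to the window ratio. The 67.5% in Table 3 pools 8-, 12- and 16-week regimens. Section 3.1.4 describes the G/P safety profile as similar across those durations, which gives no support to steady accumulation with time. If the ribavirin excess falls within the first 12 weeks, that excess is not lost; only Arm D's later background events dilute the contrast. Section 3.4 extends some 12-week subjects to 16 weeks and Section 5.4.1.1 allows more, which would narrow the gap between arms.

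*The SAP may already add exposure-adjusted rates.* Section 8.1 leaves further detail to it, and it is not at hand. Their absence from the protocol is therefore not an error. What remains is a property of the summary the protocol does specify.

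**Conclusion.** The point holds as a minor, inexpensive improvement. The windows differ by design, by 25% for AEs and 33% for laboratory shifts, and in C vs D the difference runs against seeing a ribavirin excess. Under a constant hazard the distortion is about 2 to 8 points for AEs and 3 to 10 points for laboratory shifts at Arm C percentages of 10% to 50%. That is smaller than the 13 to 22 point half-width at 40 per arm, but it is systematic and more subjects would not remove it.

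A reader might infer that the plan would hide a ribavirin toxicity signal. The documents do not support that. Only rate ratios up to about 1.25 (AEs) or 1.33 (laboratory shifts) would vanish. A ratio of 2 or 3 remains visible in the crude table, and mean hemoglobin is compared at equal times regardless. The figures rest on planned durations and an assumed constant hazard; early-onset events or treatment extensions would make them smaller.

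**What to change.** Keep the tables in Sections 8.1.4 and 8.1.5 as the summary of whole-regimen burden. Add the same AE and CTCAE-shift tables restricted to Day 1 to Week 12 on treatment in all arms, or incidence per patient-time. State that these will be used when a C vs D difference is attributed to ribavirin, or when an A vs B or C vs D difference is described as a rate per unit of treatment. If the SAP already contains such tables, a cross-reference is enough.

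Up to Week 12, Arms C and D have the same planned G/P schedule and differ only by ribavirin, so the restricted table isolates that question. Arms A and B have identical planned treatment to Week 12, so there the table shows whether a whole-regimen difference comes from the later period.

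The cost is a second set of descriptive tables from data already collected, with no new assessments. Intervals for C vs D will be wide at about 40 per arm, and the 84-day table omits later events, which is why both sets are needed.
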